#### 1. SYNOPSIS

Name of Sponsor: Sun Pharma Advanced Research Company Ltd. Name of Investigational Product: Name of active ingredient **Title of trial:** A Clinical Evaluation of the Safety of When Administered to Subjects with Spasticity due to Multiple Sclerosis (MS): An Open Label, Long Term, Safety Trial **Trial centers:** Approximately 35-40 centers Trial period: Phase of Development: 3 The trial will continue until up to approximately 250 subjects have completed at least 26 weeks of treatment, of which 200 subjects have completed at least 1 year of treatment. **Objectives:** To investigate the long term safety of when administered subjects with MS aged 18 years and above.

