#### Methodology:

This is a multicenter, open-label, safety trial in subjects with spasticity due to MS. Approximately 550 potential subjects will be screened to yield up to approximately 350 subjects enrolled from approximately 35-40 centers, in order to obtain safety data from at least 250 subjects who have completed at least 26 weeks of treatment and at least 200 subjects will have completed at least 1 year of treatment.

Subjects who enroll in this trial and participated in the double-blind phase of study CRL\_09\_21 will temporarily receive blinded study medication during the first 4 weeks which will be dispensed using an electronic drug-dispensing system (IVRS/IWRS).

All subjects will undergo safety assessments at Screening (Visit 1), Baseline (Visit 2), Week 4 (Visit 3), Week 12 (Visit 4), Week 26 (Visit 5) and all follow-up visits conducted every three months.

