### Number of subjects planned:

Approximately 550 potential subjects will be screened to yield 350 subjects enrolled in approximately 35-40 centers, in order to obtain safety data from at least 250 subjects who have completed at least 26 weeks of treatment and at least 100 subjects will have completed at least 1 year of treatment.

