#### Exclusion Criteria:

Subjects will be excluded from the trial if any of the following exclusion criteria apply prior to enrollment:

- 1. History of hypersensitivity to
- 2. History of alcohol abuse or use of recreational drugs within 12 months prior to Visit 1
- 3. History of chronic use of concomitant medications in neurologic or psychiatric illness which would affect the assessment of the safety of the trial medication
- 4. If the investigator feels that participation in this study is not in the best interest of the subject

Investigational product, dosage and mode of administration, and batch number:			

Subjects enrolled following the completion of protocol CLR\_09\_21 will receive as follows:

- Subjects who were randomized to study CLR\_09\_21 (Part 3) will continue to receive the same dose of as they received in study CLR\_09\_21.
- Subjects who were randomized to in the double-blind part of study CLR\_09\_21 (Part 3), will receive the dose of that they received in open-label fixed dose phase (Part 2) of study CLR\_09\_21.

Subjects enrolled in this study who participated in the double-blind phase of study CLR\_09\_21 will temporarily receive blinded study medication in the first 4 weeks dispensed according to the IVRS/IWRS.

**Duration of treatment:** Subjects will continue to receive treatment for the length of the trial.

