# 12. STATISTICAL PLAN

# 12.1. Sample Size

Approximately 550 potential subjects will be screened to yield 350 subjects enrolled in approximately 35-40 centers, in order to obtain safety data from at least 250 subjects who have completed at least 26 weeks of treatment and at least 100 subjects will have completed at least 1 year of treatment.

Confidential Page 34 of 47

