## 12.2. Definitions

# 12.2.1. Safety Population

The safety population will be all subjects who received at least one dose of and have subsequent contact with the clinic.

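### The planned size is stated inconsistently: the one-year minimum is 200 in some sections and 100 in others, and planned enrolment is about 350 in the Protocol but about 550 in the SAP

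*Protocol*

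**What the plan says.** **One-year completers.** The Trial period entry of the Protocol synopsis gives the only explicit end condition. It names a 26-week count of 250 and, within that count, a one-year number: "of which 200 subjects have completed at least 1 year of treatment". The Methodology paragraph of the same synopsis agrees: "at least 200 subjects will have completed at least 1 year of treatment". The next paragraph, Number of subjects planned, does not: "at least 100 subjects will have completed at least 1 year of treatment". Protocol 7.1, 8.1 and 12.1 repeat the 100. SAP 3.2 and 3.2.1 give at least 200.

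**Enrolment.** Protocol 12.1 reads "Approximately 550 potential subjects will be screened to yield 350 subjects enrolled", and the synopsis paragraph on number of subjects, 7.1 and 8.1 give the same counts. Methodology words the enrolled number as a ceiling: "screened to yield up to approximately 350 subjects enrolled from approximately 35-40 centers". SAP 3.2 and 3.2.1 use 550 for the number enrolled, and 350 does not appear in either section.

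**Related text.** SAP 2 lets the SAP override the statistical section of the Protocol where the two differ. Protocol 12.2.2 gives at least 350 enrolled and at least 100 at one year, but for an interim report at NDA submission. The Duration of treatment entry in the synopsis says "Subjects will continue to receive treatment for the length of the trial".

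**The concern.** These counts are the only statement of planned size in either document. Neither gives a power calculation, a precision target or a drop-out rate, so a reader cannot work back from a rationale to the intended number. Long-term safety is the sole objective, which makes the one-year count the central size figure. It appears at two values a factor of two apart, and the synopsis contradicts itself in consecutive paragraphs.

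The practical stake is deciding when the planned size has been reached. A team working from 7.1 or 8.1 could regard the one-year requirement as met at 100 subjects; a team working from the synopsis end condition or the SAP could not. For enrolment, a trial that recruits 350 is complete under the Protocol and 200 short under the SAP.

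**Working it through.** **1. Inputs, as printed**

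| Place | Screened | Enrolled | At 1 year |
|---|---|---|---|
| Protocol synopsis, Trial period | not given | not given | 200 |
| Protocol synopsis, Methodology | about 550 | up to about 350 | at least 200 |
| Protocol synopsis, Number of subjects planned | about 550 | 350 | at least 100 |
| Protocol 7.1, 8.1, 12.1 | about 550 | 350 | at least 100 |
| Protocol 12.2.2 (interim report) | not given | at least 350 | at least 100 |
| SAP 3.2, 3.2.1 | not given | about 550 | at least 200 |

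The 26-week number is 250 wherever it appears. Its qualifiers vary, but that is not part of this point.

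**2. Can any figure be reproduced?** No. Without an event rate, precision goal, drop-out rate or screen-failure rate, none of the counts can be derived. The check is a direct comparison plus simple ratios.

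**3. Size of the two gaps**

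- One-year minimum: 200/100 = 2.
- As a share of the 26-week number: 100/250 = 40% against 200/250 = 80%.
- Enrolment: 550 − 350 = 200, and 550/350 = 1.571, or 57% more.

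**4. The three whole-trial plans now in print**

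| Plan | Where | At 26 weeks / enrolled | At 1 year / enrolled |
|---|---|---|---|
| 350 enrolled, 200 at one year | Synopsis, Methodology | 250/350 = 71.4% | 200/350 = 57.1% |
| 350 enrolled, 100 at one year | Synopsis, Number of subjects planned; 7.1, 8.1, 12.1 | 250/350 = 71.4% | 100/350 = 28.6% |
| 550 enrolled, 200 at one year | SAP 3.2, 3.2.1 | 250/550 = 45.5% | 200/550 = 36.4% |

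These are ratios of planned counts, not retention assumptions. They mix drop-out with follow-up that ends before one year.

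**5. What the precedence clause settles.** It covers the Protocol's statistical section, so 12.1 would become 550 enrolled and 200 at one year. It does not reach the synopsis, 7.1 or 8.1. With the clause applied, 100 survives as a whole-trial figure in the synopsis paragraph on number of subjects, 7.1 and 8.1. The 350 survives in those three places and in Methodology.

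**6. Which statements a given result would meet**

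- 200 or more one-year completers: all of them.
- 100 to 199: the synopsis paragraph on number of subjects, 7.1 and 8.1 are met; the synopsis end condition, Methodology, SAP 3.2 and SAP 3.2.1 are not.
- Fewer than 100: none.
- 350 enrolled: matches the Protocol and is 200 below the SAP. 550 enrolled: matches the SAP and is 200 above the ceiling of about 350 in Methodology.

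**7. The populations differ as well.** Protocol inclusion criterion 6 (synopsis and 8.2) requires completion of Part 3 of CLR_09_21. SAP 3.1 and 3.2 also admit subjects from outside that trial, and SAP 5.1.1 sets up three Safety Groups by source. A broader planned population could carry a larger enrolment count.

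**The case against.** **At least 100 is a floor, and 200 satisfies it.** This is correct, and it limits the point. A reader might infer that the Protocol contains two competing rules for how long the trial runs. The text does not support that. Only the Trial period entry states when the trial ends, and it uses 200; the sections with 100 describe the data the plan should yield and set no stopping condition. A trial run to the stated end condition would meet every one-year figure. What remains is that the minimum is stated at two values, and a trial stopped between them would satisfy some sections and fail others.

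**The 100 is an interim milestone.** That is a fair reading of Protocol 12.2.2, which is not counted as a conflict here. The synopsis paragraph on number of subjects, 7.1, 8.1 and 12.1 carry no interim qualifier.

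**The SAP prevails.** It does for 12.1 only (step 5).

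**The 550 is a slip for the screened number.** This is plausible, because the two numbers match. The population difference in step 7 is an equally visible explanation. The documents prove neither.

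**Nothing in the analysis depends on these counts.** This stands. The SAP describes the presentations as descriptive. Membership of the analysis set depends on dosing and later contact ("The safety population will be all subjects who received at least one dose"). Disposition and exposure are reported as observed, and the subgroup thresholds in SAP 6.4 use actual subjects.

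**Conclusion.** The inconsistency is real and is in current text. The one-year minimum is 100 or 200 depending on the section, and planned enrolment is about 350 in the Protocol and about 550 in the SAP. The precedence clause removes only the 12.1 instance. This should be fixed because one of the figures sits in the trial's only explicit end condition, and because the study report could not say consistently whether the planned size was reached.

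Its weight is limited. No estimate, denominator or test changes. Neither document states a precision goal, so a reader who infers that the smaller count would fail some required precision has no basis for that in the plan.

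The conclusion assumes only that the sections without an interim label describe the whole trial, as they read. It does not assume which enrolment figure is right.

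**What to change.** 1. **One-year minimum.** Change 100 to 200 in the synopsis paragraph on number of subjects and in Protocol 7.1, 8.1 and 12.1, to match the synopsis end condition and the SAP. If the sponsor confirms that 100 is intended, restate the Trial period and Methodology entries and SAP 3.2 and 3.2.1 instead. In that case also review Protocol 12.2.2, because its interim one-year milestone would then equal the whole-trial target.
2. **Enrolment.** Have the sponsor confirm 350 or 550, then give the same screened and enrolled counts in both documents. If 550 enrolled is confirmed, the Protocol's screened count of 550 must be restated too, since it would leave no room for screen failures.
3. **Eligible population.** At the same time, reconcile Protocol criterion 6 (synopsis and 8.2) with SAP 3.1, 3.2 and 5.1.1. Aligning the counts alone could leave the cause of the difference in place.

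Once the sponsor has decided, the cost is wording in two documents. The one substantive downside is that holding to 200 may need longer follow-up than 100 would, and subjects are treated for as long as the trial runs. Choosing 100 would halve the planned number of one-year completers.

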#### Methodology:

This is a multicenter, open-label, safety trial in subjects with spasticity due to MS. Approximately 550 potential subjects will be screened to yield up to approximately 350 subjects enrolled from approximately 35-40 centers, in order to obtain safety data from at least 250 subjects who have completed at least 26 weeks of treatment and at least 200 subjects will have completed at least 1 year of treatment.

Subjects who enroll in this trial and participated in the double-blind phase of study CRL\_09\_21 will temporarily receive blinded study medication during the first 4 weeks which will be dispensed using an electronic drug-dispensing system (IVRS/IWRS).

All subjects will undergo safety assessments at Screening (Visit 1), Baseline (Visit 2), Week 4 (Visit 3), Week 12 (Visit 4), Week 26 (Visit 5) and all follow-up visits conducted every three months.

### Number of subjects planned:

Approximately 550 potential subjects will be screened to yield 350 subjects enrolled in approximately 35-40 centers, in order to obtain safety data from at least 250 subjects who have completed at least 26 weeks of treatment and at least 100 subjects will have completed at least 1 year of treatment.

# Diagnosis and inclusion/exclusion criteria:

The trial will enroll male and female subjects, at least 18 years of age, with spasticity due to MS, who meet all eligibility criteria.

Confidential Page 2 of 47

#### Inclusion criteria:

- 1. Willingness to participate and give written informed consent
- 2. Men and women  $\geq$  18 years of age
- 3. Sexually active women who are of child bearing potential will practice an acceptable method of birth control for the duration of the trial as judged by the investigator. Examples of acceptable contraception are: condoms, foams, jellies, diaphragm, intrauterine device, oral or long-acting injected contraceptives, bilateral tubal ligation, bilateral oophorectomy, hysterectomy, or having a partner who is incapable of initiating conception. The practice of contraception must have started at least 3 months prior to trial entry.
- 4. If female, negative pregnancy test result at Screening
- 5. Diagnosed with MS and a known history of spasticity
- 6. Completed the double-blind randomized withdrawal phase (Part 3) of trial CLR\_09\_21 with no major protocol violation

#### Exclusion Criteria:

Subjects will be excluded from the trial if any of the following exclusion criteria apply prior to enrollment:

- 1. History of hypersensitivity to
- 2. History of alcohol abuse or use of recreational drugs within 12 months prior to Visit 1
- 3. History of chronic use of concomitant medications in neurologic or psychiatric illness which would affect the assessment of the safety of the trial medication
- 4. If the investigator feels that participation in this study is not in the best interest of the subject

Investigational product, dosage and mode of administration, and batch number:			

Subjects enrolled following the completion of protocol CLR\_09\_21 will receive as follows:

- Subjects who were randomized to study CLR\_09\_21 (Part 3) will continue to receive the same dose of as they received in study CLR\_09\_21.
- Subjects who were randomized to in the double-blind part of study CLR\_09\_21 (Part 3), will receive the dose of that they received in open-label fixed dose phase (Part 2) of study CLR\_09\_21.

Subjects enrolled in this study who participated in the double-blind phase of study CLR\_09\_21 will temporarily receive blinded study medication in the first 4 weeks dispensed according to the IVRS/IWRS.

**Duration of treatment:** Subjects will continue to receive treatment for the length of the trial.

#### Criteria for evaluation:

Efficacy: This is a safety trial. Efficacy will not be formally evaluated.

**Safety:** The following safety parameters will be evaluated:

Confidential Page 3 of 47

- Treatment Emergent AEs and concomitant medication assessments
- Vital signs (seated blood pressure and pulse)
- Clinical laboratory tests
- 12 lead electrocardiogram (ECG)
- Physical examination and neurological evaluation
- Columbia-Suicide Severity Rating Scale (C-SSRS)

## Statistical methods:

Descriptive statistics, including the numbers, means, standard deviations, medians, minimums, maximums and 95% confidence intervals for continuous variables and the numbers and percentages for categorical variables, will be provided. Listings of individual subject's data will also be produced.

Subset analysis will be stratified by concomitant anti-spasticity and MS medication used if the percentage of subjects in these stratification groups is  $\geq 10\%$  of the total number of subjects enrolled.

Confidential Page 4 of 47

	Day -14	Day 1	Day 28	Day 84	Day 182	
Activities	Week -2 Visit 1 (Screen) a	Week 1 Visit 2 (Baseline)	Week 4 ± 5 days Visit 3	Week 12 ± 5 days Visit 4	Week 26 ± 5 Days Visit 5 / Premature Termination Visit b	Visits Every 3 Months ± 5 days c
Informed consent	X	-	-	-	-	
Medical history and demographics	X	-	-	-	-	
Physical examination	X	-	-	-	X	
Neurologic examination	X	-	-	-	X	
Urine pregnancy test	X	-	X	X	X	X
Vital signs (sitting)	X	-	X	X	X	
Clinical laboratory tests d	X	-	-	-	X	
12-lead ECG e	X	-	X	X	X e	
C-SSRS	X	-	X	X	X	X
Concomitant medication and physical therapy assessments	X	X	X	X	X	X
AE evaluation	X	X	X	X	X	X
Dispense study medication	X	X	X	X	X	X
Collect study medication	-	X	X	X	X	X
Dispense / collect subject diaries	X	X	X	X	X	X
6 1 1 1 · · · · ·	77	37	7.7	7.7	77	***

Table 1: Visits and Procedures Schedule

X

X

Χ

X

X

X

Schedule next visit

Confidential Page 5 of 47

aScreening Visit assessments in CLR\_11\_04 which are identical to final visit assessments in CLR\_09\_21 do not need to be repeated. The Screening Visit may be completed simultaneously with the final visit for CLR\_09\_21, and on the following day, if needed, provided drug supply from CLR\_09\_21 does not run out. Subjects cannot enter CLR\_11\_04 if drug supply runs out prior to the completion of the screening process.

<sup>bFor subjects not completing the study, all activities scheduled at this visit are to be conducted during the Premature Termination visit with the exception of the ECG (see footnote "e" below) and the physical and neurologic examinations. These three assessments may be conducted during the Premature Termination visit as needed in order to follow the resolution of any adverse events.

<sup>cThese visits will be scheduled 90 (± 5) days following the previous visit.

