#### 8.4. Withdrawal Criteria

The subject will receive oral and written information about the trial, which includes information about the right to withdraw from the trial at any time without prejudice to future treatment. In this case, the subject must immediately contact the investigator and inform the investigator that he/she is leaving the trial. The subject will be encouraged to provide the reason for wishing to withdraw. The subject must return the trial drug as well as undergo early study termination procedures.

The investigator must withdraw a subject from the trial in the following cases:

Occurrence of an AE which does not justify a continuation of the trial in that subject

Confidential Page 21 of 47

Major protocol violation which jeopardizes the interpretation of that subject's data

The following are additional justifiable reasons for removing a subject from the trial:

- Subject experiences intolerable spasticity
- Subject has a treatment related SAE
- Subject becomes pregnant during the trial
- If, in the investigator's opinion, continuation in the trial would be detrimental to the subject's well being

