# 9.6. Withdrawal From the Study

#### 9.6.1. Premature Discontinuation of Subject in the Trial

The investigator will make every effort to keep each subject in the study. However, should a subject be removed from the study or elect to decline further study participation, the information will be recorded on the appropriate page in the eCRF, and the primary reason for discontinuation will be selected: 1) adverse event; 2) major protocol violation; 3) lost to follow-up; 4) worsening of clinical condition or loss of efficacy; or 5) other (for which the reason should be clearly stated).

As far as possible, all assessments and procedures scheduled for the end-of-trial visit must be performed on all subjects who receive trial medication but do not complete the trial according to protocol. The subject must return all unused investigational products.

Subjects who are withdrawn from the trial due to AEs will be treated according to established acceptable medical practice and will be followed for outcome. All pertinent information concerning the outcome of such treatment will be entered in the eCRF.

The investigator will make every effort to contact subjects lost to follow-up.

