# 10.5. Visit 5 (Day 182 $\pm$ 5 days/Week 26), or Premature Termination

- Physical and neurologic examinations will be performed during Visit 5, but will be performed as needed during the Premature Termination visit to follow the resolution of any adverse events
- A urine pregnancy test will be performed
- Vital Signs (sitting), after resting for 5 minutes, will be obtained
- Clinical laboratory testing will be performed including hematology (RBC count, hemoglobin, total and differential WBC count, platelet count), and serum chemistry including sodium, potassium, chloride, BUN, and creatinine
- A 12-lead ECG will be performed in triplicate. 12-lead ECG should be performed at the Premature Termination visit, as needed, in order to follow adverse events to resolution.
- C-SSRS assessment will be performed
- Concomitant medication and physical therapy will be recorded
- AEs will be recorded
- Study medication and Subject diary collected and reviewed from previous visit for compliance
- Study medication and subject diary will be dispensed
- The next trial visit will be scheduled.

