# 10.6. Visits Every 3 Months after Visit 5 (90 $\pm$ 5 days following Visit 5 and all subsequent visits)

- Concomitant medication and physical therapy will be recorded
- AEs will be recorded
- A urine pregnancy test will be performed
- C-SSRS assessment will be performed
- Study medication and Subject diary will be dispensed (for subjects continuing on treatment only)

Confidential Page 26 of 47

- Study medication and Subject diary collected and reviewed from previous visit for compliance
- The next trial visit will be scheduled

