3.2.3 Study Assessments Schedules

Study assessments are described in detail in the protocol, and summarized below in Table 1.

Table 1: Visits and Procedures Schedule

	Day -14	Day 1	Day 28	Day 84	Day 182	
Activities	Week -2 Visit 1 (Screen)	Week 1 Visit 2 (Baseline)	Week 4 ± 5 days Visit 3	Week 12 ± 5 days Visit 4	Week 26 ± 5 Days Visit 5 / Premature Termination Visit ^b	Visits Every 3 Months ± 5 days ^c
Informed consent	X	-	-	-	-	
Medical history and demographics	Х	-	-	-	-	
Physical examination	X	-	-	-	X	
Neurologic examination	X	-	-	-	X	
Urine pregnancy test	X	-	X	X	X	X
Vital signs (sitting)	X	-	X	X	X	
Clinical laboratory tests ^d	X	-	-	-	X	
12-lead ECG ^e	X	-	X	X	Xe	
C-SSRS	Xf	-	X	X	X	X
Concomitant medication and physical therapy assessments	X	X	X	X	Х	X
AE evaluation	Xs	Χs	X	X	X	X
Dispense study medication	Xh	X	X	X	X	X
Collect study medication	-	X ⁱ	X	X	X	X
Dispense / collect subject diaries	Xj	Х	X	Х	Х	X
Schedule next visit	X	X	X	X	X	X

^{*}Screening Visit assessments in CLR_11_04 which are identical to final visit assessments in CLR_09_21 do not need to be repeated. The Screening Visit may be completed simultaneously with the final visit for CLR_09_21, and on the following day, if needed, provided drug supply from CLR_09_21 does not run out. Subjects cannot enter CLR_11_04 if drug supply runs out prior to the completion of the screening process.

SAEs recorded for subjects entering from clinical trial CLR 09 21only

For subjects not completing the study, all activities scheduled at this visit are to be conducted during the Premature Termination visit with the exception of the ECG (see footnote "e" below) and the physical and neurologic examinations. These three assessments may be conducted during the Premature Termination visit as needed in order to follow the

Hematology: red blood cell (RBC) count, hemoglobin, total white blood cell (WBC) count, differential WBC count, platelet count; serum chemistry: sodium, potassium, chloride, blood urea nitrogen (BUN), creatinine.

^{*}Completed in triplicate two minute intervals during Visit 5. 12-lead ECG should be performed at the Premature Termination visit, as needed, in order to follow adverse events to resolution

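### As written, the Premature Termination visit has sites dispense study medication and a diary and book a next visit, which conflicts with the withdrawal and drug-return rules

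*Protocol*

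**What the plan says.** Protocol Table 1 has a single column headed "Visit 5 / Premature Termination Visit", and the row for dispensing study medication is marked in it. Footnote b governs subjects who do not complete: "all activities scheduled at this visit are to be conducted during the Premature Termination visit with the exception of the ECG". It goes on to add the physical and neurologic examinations to the exceptions, and says of the three: "These three assessments may be conducted during the Premature Termination visit as needed in order to follow the resolution of any adverse events".

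Protocol Section 10.5 covers Visit 5 or Premature Termination in one list. It includes "Study medication and subject diary will be dispensed" and a line for scheduling the next trial visit. Neither carries a condition.

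Three other sections point the other way:

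- Section 8.4, on a subject who leaves: "The subject must return the trial drug as well as undergo early study termination procedures".
- Section 9.6.1, on premature discontinuation: "The subject must return all unused investigational products".
- Section 10.6, on the three-monthly visits after Visit 5: "Study medication and Subject diary will be dispensed (for subjects continuing on treatment only".

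SAP Table 1 (SAP Section 3.2.3) reproduces the protocol schedule. It has the same shared column, marks both dispensing and scheduling the next visit in it, and carries the same footnote: "all activities scheduled at this visit are to be conducted during the Premature Termination visit".

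**The concern.** A site that follows Table 1 with footnote b, or Section 10.5, would collect the old supply from a subject who is leaving, issue a new one with a diary, and book another visit. A site that follows Sections 8.4 and 9.6.1 would take the drug back and end participation. Both instructions are in force, and no visible text says which prevails.

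The subjects concerned include those withdrawn for an adverse event. They may include those removed for a treatment-related serious adverse event or for pregnancy, both of which Section 8.4 lists as grounds for removal.

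This is a safety trial, so the point also touches the data. SAP Section 6.3.1 captures adverse events until 30 days after the end of the trial and tabulates treatment-emergent events by dose at onset. If drug is issued at exit, the dose at onset of a late event may not be known. SAP Section 6.1.6.1 ends exposure at the last-dose date on the final status eCRF or, if that is missing, at the last visit with a drug return. In the second case, capsules taken after exit could go uncounted.

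**Working it through.** No arithmetic applies, and the plan states no figure to reproduce. The check is to set the provisions side by side.

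1. Which items footnote b removes. It names three: ECG, physical examination and neurologic examination. Everything else marked in the shared column stays, including dispensing study medication and the combined row for dispensing and collecting diaries.

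2. Whether Section 10.5 narrows this. It adapts the examinations and the ECG for early terminators, so its drafters had those subjects in mind. It does not adapt the lines on dispensing drug, dispensing the diary or scheduling the next visit.

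3. Whether the finding depends on a damaged table. The row for scheduling the next visit is broken in the protocol text available for review. Section 10.5 and SAP Table 1 both state the item clearly, so nothing rests on that row.

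4. Where each item conflicts:
   - Dispensing drug conflicts with Sections 8.4 and 9.6.1, because a subject who has returned everything and then receives a new supply again holds unused product. It also sits badly with Section 10.6, and with Section 13.3, which restricts supply to subjects participating in the protocol.
   - Dispensing a diary conflicts with the Section 10.6 limit, which covers the diary as well as the drug. Collecting the old diary at exit raises no difficulty.
   - Scheduling a next visit conflicts with leaving the trial, not with the return of drug.

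5. Whether another provision settles it. The Section 10.6 qualifier applies only to visits after Visit 5. Section 9.6.1 asks that end-of-trial procedures be done, as far as possible, for subjects who stop early, which sends the reader back to the same list. SAP Section 2 gives the SAP precedence over the statistical section of the protocol only, and SAP Table 1 has the same conflict anyway.

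6. What this does to the analysis rules. The reported last-dose date is used when it exists, and nothing confines that date to the exit visit. Exposure is therefore uncertain only when the date is missing. Under SAP Section 6.1.6.2, compliance is calculated for the bottles dispensed at each visit. A bottle issued at exit and not returned would leave only the post-exit interval missing; the on-study intervals rest on earlier bottles, which the same column has the site collect.

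**The case against.** The strongest reply is that sites would not act on this. The return rules are specific, Section 11.3.3 ends participation after a positive pregnancy test, and Section 10.6 shows that dispensing was understood to be for continuing subjects. That makes a drafting error the likely explanation. It does not remove the conflict: the list of exceptions is explicit and leaves dispensing out, and since collection is marked in the same column, a site could take back old drug, issue new drug and believe it had complied.

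A second reply is that the harm needs one line taken literally and the next ignored. If the next visit really is scheduled, drug is collected there, so a bottle issued at exit does have a planned return. This stands against any claim that such bottles necessarily go unaccounted for. But that literal reading keeps a withdrawn subject on the supply schedule, which is itself the contradiction.

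A third is that the treatment-dose and packaging sections are largely not shown, and some SAP Table 1 markers have no visible footnote. Those markers sit in the screening and baseline columns, so they probably do not bear on this. Text on supply after exit could exist in what is not shown; the visible sections would still need to agree with it.

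**Conclusion.** The contradiction holds. Table 1 with footnote b, Section 10.5 and SAP Table 1 direct three things at Premature Termination (drug dispensing, diary dispensing and a next visit) that do not fit Sections 8.4, 9.6.1 and 10.6. It should be corrected because it decides who leaves the trial with study drug.

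The consequence for the analysis is conditional. Dose at onset could be uncertain for adverse events in the 30 days after the end of the trial, and the end of exposure could be uncertain where no last-dose date is reported. This assumes that a site follows the schedule as written and that the subject takes the drug issued. Sample size and error rates are unaffected.

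Stronger readings are tempting but not supported:

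- A reader might take 350 enrolled and 250 completing 26 weeks to mean that (350 - 250)/350 = 29% would be affected. The 350 is approximate, the 250 is mostly stated as a minimum, SAP Section 3.2.1 gives about 550 enrolled, and no dropout rate is stated.
- A reader might infer about three months of supply per subject from the 90-day visit interval. No dispensed quantity is visible.
- A reader might apply this to every early terminator. Subjects lost to follow-up may never attend the visit.
- A reader might conclude that exposure is necessarily lost or that compliance data are damaged. The SAP rules on the last-dose date and on compliance by visit do not support either.

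**What to change.** Reconcile Protocol Table 1 footnote b and Section 10.5 with Sections 8.4, 9.6.1 and 10.6, and make the same change in SAP Table 1. For the Premature Termination visit, state whether drug dispensing, diary dispensing and scheduling of the next visit apply. Separate diary dispensing from diary collection, which now share a row.

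- If the three items do not apply, add them to the footnote b exceptions and carry a qualifier like that of Section 10.6 into Section 10.5.
- If some supply after that visit is intended, say so, and state how it is returned and how it enters the last-dose date.

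Which of these is right is a clinical decision for the sponsor. The cost is wording in one footnote, a few list lines and the matching SAP table at the next amendment. Stating the rule adds no procedure.
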